## 2. The Trial

### 2.1 Trial design

This is a double-masked, placebo-controlled 28-day (4-week) baseline, 84-day (12-week) experimental trial, enrolling 175 women and stratifying random therapy assignment by Early or Late Perimenopause.

### 2.2 Trial interventions

The proposed trial intervention is OMP, 300 mg/day (Experimental) or matching placebo (Control), each taken as three capsules daily before sleep. This is important because OMP should not be taken during waking hours because of its soporific effects . The dose of 300 mg of OMP is a physiological one that maintains the serum progesterone at or above the luteal (normal post-ovulatory) threshold for 24 hours .

Placebo-control of trials are required for VMS therapy because of the well-known response to placebo treatment, estimated by meta-analysis of RCT studies as 50.8% improvement (95% CI 41.7-58.5) . Postmenopausal women randomized to placebo in our randomized trial showed a 22% reduction in VMS Score (daytime VMS number X intensity plus nighttime VMS number X intensity) from baseline . Also, there are no effective therapies to use for an active comparison. There is an additional reason to include a placebo control for a VMS trial with perimenopausal women, because the natural history is for hot flushes to be variable and to increase over time to a maximum during the final year without flow .

### 2.3 Allocation of participants within the trial

Random allocation will be stratified by phase of perimenopause (Early, <60 days cycle length, versus Late, having had at least one  $\geq 60$  day long menstrual cycle). Two lists of random numbers will be computer-generated by a statistician not associated directly with the study. Permuted blocks of size 10 will be used. A research pharmacist will access appropriate (Early or Late Perimenopause) lists from this computer webpage to determine whether to dispense Experimental or Control therapy.

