### 2.4 Protecting against bias

Neither participants nor research staff (including the research coordinator, and anyone directly related to the trial) will know who received Experimental or Control therapies. The only person directly interacting with participants who will know the therapy assignment will be the research pharmacist. Progesterone and placebo will be provided as white coloured, round capsules, identical except for the active ingredient. Investigators will remain masked until all participants have completed the study and the data have been entered, cleaned and checked.

As each participant completes her participation, the research pharmacist will provide her with a letter disclosing her therapy assignment, with instructions to not disclose it to the researchers. (Although therapy assignment is conventionally withheld from participants until study completion, we feel that participants need this information to make informed choices about active therapy following their participation and before the end of the study. By providing women with copies of their own diary data and their therapy group assignment, we allow them, in a timely manner, to directly benefit from study participation. We have found this an additional incentive for study participation.)

Besins Healthcare, providers of drug and placebo, will have no role in the design, conduct, analysis or publication of the study.

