## **2.11 Sample size**

The **proposed sample size is 175 women**, to be stratified into Early and Late Perimenopause and randomized equally to active therapy or placebo. Previous analysis of similar VMS Score data from menopausal breast cancer therapy studies  concluded that a VMS Score difference of 3 is clinically important, which supports our recent estimate of 2.7 for the minimal important difference in perimenopausal women using the interpersonal assessment methods of Redelmeier  ([name] & [name], unpublished MS). This corresponds to an effect size of 0.58 . We anticipate more VMS variability in perimenopause than in postmenopause, and thus a smaller effect size. The sample size of 175 reflects an anticipated discontinuation rate of 20% (as in our past progesterone trial for VMS in postmenopausal women), and an effect size of 0.48 (revised to allow for 20% greater SD in perimenopausal women above that in postmenopause), an alpha of 0.05 using a two-tailed test and having a power of 0.80 to detect a significant difference between two groups (calculations using GPower3).

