### **3. Trial Management**

#### **3.1 Arrangements for day-to-day management of the trial**

A research coordinator for the study will handle the day-to-day tasks of responding to potential participants who enquire, assessing eligibility, teaching them how to complete the Calendar and interviewing them. The research coordinator will be under the direct supervision of the principal investigator and will meet with her regularly at no less than two week intervals.

When participants have completed the baseline assessment and their symptoms meet randomization criteria, they will be given a prescription for masked study medication which also has information on their Early or Late Perimenopause status. The pharmacist will access the web-based treatment allocation programme to obtain the next randomly selected allocation (see section 2.3 for details), and dispense either OMP or placebo to the participant. For remote participants, the research coordinator will go the study pharmacy on the participant's behalf and send the medication by courier.

Should there be a medical need to determine the therapy assignment for a participant during the study, [name], who is not directly involved with participants, will address any relevant clinical concerns. [name] or [name] who are also not directly involved with participants, will act as back-up in the event [name] is unavailable.

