## 4. Assessment of Safety

An **Adverse Event** will be defined as follows:

Any untoward medical occurrence in a participant administered a pharmaceutical product and which does not necessarily have to have a causal relationship with this treatment.

A **Serious Adverse Event** will be defined as follows:

A serious adverse event (experience) or reaction is any untoward medical

occurrence that at any dose:

- results in death,
- is life-threatening,
- requires inpatient hospitalization or prolongation of existing hospitalization,
- results in persistent or significant disability/incapacity, or
- is a congenital anomaly/birth defect .

Adverse events will be assessed throughout study participation through direct questioning of study participants, by specific study-end questionnaires and will all be followed to resolution.

All serious adverse events will be assessed by the principal investigator, reported to the DSMC and the local research ethics board, and be followed to resolution. Adverse Drug Reactions will be reported to Health Canada per applicable regulatory guidelines. For study data purposes, period of capture for serious adverse events and adverse drug reactions will be from first, up to and including last day of study treatment.

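### A single stated block size of 10, with each woman told her arm as she finishes, makes leaked assignments partly informative about others in her block; the risk is small unless leaks are frequent

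*Combined protocol and SAP*

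**What the plan says.** Section 2.3 describes the lists: "Two lists of random numbers will be computer-generated by a statistician not associated directly with the study", one for Early and one for Late Perimenopause. It then states "Permuted blocks of size 10 will be used" and names no other size. Section 2.11 has women "randomized equally to active therapy or placebo", so each block holds five of each arm.

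Section 2.4 provides for rolling disclosure. At completion, "the research pharmacist will provide her with a letter disclosing her therapy assignment, with instructions to not disclose it to the researchers". The same section requires that "Investigators will remain masked until all participants have completed the study and the data have been entered, cleaned and checked". It acknowledges that assignments are usually withheld until a study ends, and gives its reason for departing from this: women should be able to make informed treatment choices afterwards.

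Staff can follow the order of entry within a stratum. Under section 3.1, once women qualify after baseline, "they will be given a prescription for masked study medication which also has information on their Early or Late Perimenopause status". The coordinator also collects the medication for remote participants. Contact with a woman can continue after she has her letter, because section 4 says that adverse events "will all be followed to resolution".

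**The concern.** Sections 2.3 and 2.4 are each defensible alone. Together they open a route by which assignments known to women who have finished can bear on women who have not. A person who knows the block size, the order of entry within a stratum and some finished women's arms can update the odds for the rest of that block. The only stated barrier between the letter and the staff is an instruction to the participant.

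What is at stake is staff masking. The coordinator assesses eligibility (3.1), may ask for a further baseline month (2.13) and contacts each woman monthly on treatment (2.13). The principal investigator assesses serious adverse events (4). Partial knowledge of assignment could colour any of these. The primary outcome comes from the diary of a woman who is herself still masked, so it is exposed only indirectly.

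**Working it through.** The plan states no figure for predictability, so there is none to reproduce. The sample size of 175 (2.11) does reproduce: effect size 0.48, two-sided 0.05 and power 0.80 give 70 per arm by the t-test, and 140/0.80 = 175. It does not bear on this point, nor does the later goal of 245.

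**Inputs from the protocol.** Blocks of 10 in two lists (2.3); equal allocation (2.11); 84 days of treatment before a letter is issued (2.6); projected enrolment of 20 in six months, then 60, then 75 a year (2.12).

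**Assumptions.** An even Early/Late split; all enrolled women randomised; no drop-out; leak rates from 10% to 100%; each leak reaches, at once, someone who tracks order and block boundaries.

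**Within one block.** If k assignments are known, a of them on a given arm, the chance that another member is on that arm is (5 − a)/(10 − k).

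- One leak: the other arm has probability 5/9 = 55.6%.
- Two, three, four or five leaks, all of the same arm: 5/8 = 62.5%, 5/7 = 71.4%, 5/6 = 83.3%, 5/5 = 100%.
- So certainty needs at least five same-arm leaks from one block. Five random leaks all fall on one arm with probability 2/C(10,5) = 2/252 = 0.8%.

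**Ceiling, with every earlier assignment in the block known.** The best guess is right (5 + 2^9/C(10,5) − 0.5)/10 = (5 + 512/252 − 0.5)/10 = 65.3% of the time. The expected number of forced assignments is 2×5/(5 + 1) = 1.67 per block, or 16.7%. Fixed known blocks of 4 would give 70.8% and 33.3%, so 10 is one of the less predictable sizes.

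**Women on treatment.** Simulated knowledge by the end of a woman's own treatment, with random arrivals:

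| Leak rate | Best guess right | Guessable at 70% or better | Certain |
|---|---|---|---|
| 10% | 52% | 0.2% | 0% |
| 25% | 54% | 2% | under 0.1% |
| 50% | 57% | 7% | 0.6% |
| 100% | 65% | 25% | 17% |

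Repeat runs lie between 0.1 and 0.2% for the 10% row and between 6 and 7% for the 50% row (third column).

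**Women not yet randomised.** The 84-day delay lets much of a block fill before its first letter. With an even split, each stratum randomises 20, 30 and 37.5 women a year in years 1 to 3. In 84 days that is 20×84/365 = 4.6, 30×84/365 = 6.9 and 37.5×84/365 = 8.6 women. The share guessable at 70% or better is:

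| Women per stratum per year | Half leak | All leak |
|---|---|---|
| 37.5 | 0.2% | 0.7 to 0.8% |
| 30 | 0.5% | 1.8 to 1.9% |
| 20 | 1.5% | 5% |
| 15 (slower than projected) | 2% | 7 to 8% |

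**The case against.** The strongest reply is that the instruction in 2.4 may work. The documents report no leak, and the large figures need most women to ignore a written request and someone on the staff to keep a tally by stratum. The letter is described for women who complete, and 2.14 expects 20 to 25% to discontinue, which makes full disclosure less likely still. An independent statistician makes the lists and a pharmacist draws from them. The end-of-treatment figures also overstate what is known at the earlier monthly contacts. The sponsor considered early disclosure and gave a reason for it. All of this stands, and it is why the point is minor.

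It does not remove the point. The barrier is behavioural, the fixed size adds to whatever leaks do occur, and varying the sizes would have cost almost nothing at the planning stage.

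Three stronger readings are tempting, and the documents do not support them.

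- A reader might infer that any leaked assignment gives away those of other women. One leak shifts a block-mate by 5.6 percentage points and settles nobody's arm.
- A reader might infer that concealment before randomisation is badly compromised. At the rates projected for years 2 and 3 the exposure is about 2% or less even if every assignment leaks. It is higher at the first-year rate or slower. Section 2.15 reports a recruitment shortfall but not its size.
- A reader might infer that the block size was public during recruitment. The ethics board chair's letter calls the protocol posted, without saying whether that was so while women were being enrolled. Staff working from the protocol would know the size either way.

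**Conclusion.** The point holds as a low-cost improvement to masking. It is not a threat to the trial's main result. A stated, fixed block size of 10 together with disclosure at completion makes leaked assignments partly informative about other women in the same stratum and block, mainly those still on treatment. By the end of treatment, about 0.1 to 0.2% of women are guessable at 70% or better with 10% leakage and about 6 to 7% with half. The 17% certain applies only if every assignment leaks. These sizes rest on assumed leak rates, an even split between strata and an observer who tracks order perfectly. The last assumption makes them upper figures for each leak rate. Nothing in the documents shows that a leak occurred or that any decision was affected.

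**What to change.** In 2.3, have the independent statistician generate each stratum's list with randomly varying block sizes that average no less than 10, for example 8, 10 and 12. Keep the sizes in a document that trial staff do not see, and remove the number from the protocol. The completion letters in 2.4 can stay.

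The average size matters. For an observer who knows the set of sizes but not their sequence:

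| Sizes | Certain, all leak | Best guess right, all leak | 70% or better, half leak |
|---|---|---|---|
| Fixed 10 | about 17% | 65% | 6 to 7% |
| 8, 10, 12 | about 1% | 65% | 1 to 2% |
| 4, 6, 8 | about 2% | 68% | 8% |

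Smaller mixed blocks therefore remove most certainty but make average guessing easier. The larger mix has one limit: if every assignment leaked, guesses at 70% or better would rise from about 25% to 36%, in exchange for losing nearly all the certain ones. At the more plausible lower leak rates it is better on both counts.

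The cost is a slightly larger possible imbalance at the end of each list: at most 6 with a block of 12, against 5 with a block of 10. The ethics board letter of November 2018 describes the database as locked and analysed, so the lists cannot be changed for this trial. Here the block size and the rolling disclosure should be reported as a limitation on staff masking. The change itself applies to any repeat of the design.

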### 2.4 Protecting against bias

Neither participants nor research staff (including the research coordinator, and anyone directly related to the trial) will know who received Experimental or Control therapies. The only person directly interacting with participants who will know the therapy assignment will be the research pharmacist. Progesterone and placebo will be provided as white coloured, round capsules, identical except for the active ingredient. Investigators will remain masked until all participants have completed the study and the data have been entered, cleaned and checked.

As each participant completes her participation, the research pharmacist will provide her with a letter disclosing her therapy assignment, with instructions to not disclose it to the researchers. (Although therapy assignment is conventionally withheld from participants until study completion, we feel that participants need this information to make informed choices about active therapy following their participation and before the end of the study. By providing women with copies of their own diary data and their therapy group assignment, we allow them, in a timely manner, to directly benefit from study participation. We have found this an additional incentive for study participation.)

Besins Healthcare, providers of drug and placebo, will have no role in the design, conduct, analysis or publication of the study.

## 2.5 Inclusion/exclusion criteria

To make the study as widely generalizable as possible, the study inclusions are broad and there are minimal exclusions:

### **Inclusion:**

- $\geq 35$  to  $\leq 58$  years of age
- At least 4 VMS per day on average, for at least two weeks of every four-weeks, or at least 56 over a four-week period. In addition, women should report having VMS that of moderate or severe rather than of mild intensity. Women reporting fewer VMS than this, but who report night sweats that awaken them from sleep on two or more nights per week will also be included, because we believe that VMS that disturb sleep are clinically important.
- Perimenopausal status either based on irregularity of menstrual periods, or by onset of new perimenopausal symptoms in women with regular periods  (as described earlier).
- At least one menstrual period within 12 months of study enrollment
- Ability and willingness to complete the Daily Perimenopausal Hot Flush Calendar recording instrument.
- Ability to understand, speak, read and write English.
- Women who are at high risk for breast cancer (ie first degree relative with breast cancer, known/suspected history of breast cancer) will be required to have a normal mammogram and clinical breast examination within 12 months of study enrollment.

### **Exclusion:**

- VMS without perimenopausal etiology
- Women who have had a hysterectomy,  $\pm$  ovariectomy
- Peanut allergy (because peanut oil is used in the progesterone formulation)
- Current or recent (within 6-mo of study enrollment) use of hormonal therapies (estrogen, progesterone, hormonal contraceptives, hormonal fertility treatments), or plans to initiate use during the study period. Two exceptions will be made. The first is women using a progestin-releasing intrauterine device (IUD) will not be excluded as it is felt that the level of hormone released will not have an effect on VMS. The second is women taking very low-dose transdermal progesterone therapies who have VMS and meet inclusion criteria will be considered for inclusion on a case-by-case basis. If enrolled, they will be required to continue and document use of this very low-dose hormone therapy throughout the entire trial.
- Planned pregnancy or fertility treatment during the study period
- Women who are breastfeeding
- Participants with a score of  $\geq 15$  on the Personal Health Questionnaire (PHQ-9) will be assessed on a case-by-case basis. Women assessed as needing further investigation and/or treatment for depression will be excluded.

## **2.6 Duration of the experimental period**

The treatment period is 12-weeks (84 days). This is conventional for VMS treatment trials, and is recommended by the FDA for VMS studies for postmenopausal women.

## **2.7 Frequency and duration of participant follow up**

*Screening* Study enquirers will be screened initially by telephone.

Subsequent study visits will occur in-person or through remote participation; this differentiation will be recorded in the study database. Procedures are identical for both types of participation except that communication for remote participation will be through web-conference (Skype), telephone, email or mail. Participants returning study documents and medication via mail will be provided with postage-paid envelopes. Faxes will be received into confidential fax machines.

### *Initial Visit*

Women will review the consent form sent by email, fax or mail. Eligible women who remain interested will be seen in person, sign informed consent, receive a fully executed copy of the consent, complete questionnaires and be taught to keep the Daily Perimenopause Hot Flush Calendar ('the Calendar.') Instructions for completing the Calendar will be included on the Calendar form. With remote participation, verbal consent will be obtained, the participant will email, fax, mail the signed consent. As measures of good health practice, breast self-examination will be taught, women will be encouraged to perform this monthly and women will be provided with a handout on osteoporosis prevention.

### *Randomization Visit (one month after initial visit)*

The Calendar data will be assessed for completeness and clarity. Participants will complete some health questionnaires. Based on self-report of maximum menstrual cycle length during the previous year, women will be stratified to Early (<60 days) versus Late Perimenopause ( $\geq 60$  days). This information will be provided with a prescription to the study pharmacy so they can be randomized to Experimental or Control therapy. With remote participation the research coordinator will obtain study medication on the participant's behalf and send it to the participant via courier.

### *Monthly follow-up while on study treatment*

During study treatment period, women will be contacted by telephone or e-mail monthly to assess their progress, monitor for safety and to answer any of their questions.

### *Final Visit*

Women will return completed Calendar forms, complete questionnaires, return any remaining study medication. Returned pills will be counted and/or Calendar recording will be reviewed, to assess adherence and ensure drug accountability. The final questionnaire may be emailed/faxed/mailed to the participant for completion the day following last dose of study treatment, in the event the final visit cannot be scheduled for this date.

## **2.8 Primary and secondary outcome measures**

The primary outcome will be assessed from prospective records using the Daily Perimenopause Hot Flush Calendar. The Calendar is a one-page chart with a vertical column for each day of the month that includes flow, sleep problems and anxiety as well as VMS (attached). Items are rated

on 5-point scales or as counts, as appropriate. Daily VMS frequency and severity are recorded separately for hot flushes during the individual's waking or work day and night sweats that occur during sleep. Uniformity of training will be addressed through standardized verbal and written instructions.

## **PRIMARY OUTCOMES**

1. Vasomotor Symptoms (VMS) – VMS Score, computed from prospective daily Calendar ratings of night sweat frequency and severity and hot flush frequency and severity as :

**Daily VMS Score** = (# night sweats) x (severity) + (# hot flushes) x (severity) and summarized as a daily average during the final 28 days of therapy with average run-in scores as a covariate. This composite score has the advantage that it includes both number and intensity during the waking day and during sleep. However, this score assumes that two moderate episodes are equivalent to a single very intense episode, which may or may not be the case.

Subgroup analysis for those with frequent and severe VMS: To complement this analysis, we will do a subgroup analysis of the number and VMS Score for those with more frequent ( $\geq 7/d$  and moderate to severe episodes of intensity  $\geq 2$ ) at baseline.

2. Frequency and Severity (0-4) of VMS, evaluated from prospective daily Calendar ratings as a daily average during the final 28 days of therapy with average run-in scores as covariates.

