#### Clinical trials of progestin or progesterone therapy in postmenopause

We have recently (Oct 2009) completed a randomized, masked, placebo-controlled trial of OMP for VMS in healthy postmenopausal women. This is the only trial of OMP for VMS of which we are aware. We found significantly more improvement in those randomized to OMP (Prometrium®, 300 mg at bedtime daily) therapy than to placebo: (52% vs. 22%) improvement in VMS Score, and greater decreases in daily VMS frequency (44% vs. 17%) and severity (38% vs. 19%). Significant therapy by baseline interactions indicated that those who had more frequent/intense VMS at baseline showed greater treatment benefits from progesterone compared with placebo, for both VMS Score and VMS Frequency. This analysis considered all randomized women for whom we had daily diary records of VMS (n=127); for 13 of these, we used last observation carried forward to impute the final score.

Considerable RCT evidence is available showing the effectiveness of medroxyprogesterone (MPA), the most biochemically similar progestin to OMP, either orally or as a depo-injection for the treatment of VMS. Furthermore, a parallel double-masked 1-yr trial (begun in the 1980s when these were the dominant hormonal therapies) of conjugated equine estrogen (Premarin®, 0.6 mg/d) compared with MPA (Provera®, 10 mg/d) found equivalently effective control of the expected increase in VMS following bilateral ovariectomy in premenopausal women. The three published trials of transdermal progesterone cream (Pcream) for VMS in menopausal women showed contradictory results—one with 20 mg/d over one year showed significant improvement while a 12-week trial of 32 mg/d Pcream showed no significant effect, and a dose-response trial tended to show benefit at the highest dose.

Neither our searches nor those of others recently reviewing the literature have uncovered any further controlled clinical trials investigating progestins or progesterone as therapy for postmenopausal VMS.

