#### **2.16 Statistical analysis**

The analysis will use analysis of covariance (ANCOVA) of the final outcome variable by therapy assignment, phase of perimenopause (Early/Late) and the interaction of therapy with phase, with baseline outcome variable as a covariate. The interaction term will assess the possibility that the response to therapy differs between those in Early and Late Perimenopause. For Daily Perimenopause Diary or Calendar VMS data, two 28-day (4-week) averages will be compared: immediately prior to therapy assignment and the final 4-weeks of the treatment phase. For questionnaires, the scores from pre-randomization and final visits will be used. The

assumptions of parametric analysis will be checked, and data will be either transformed prior to analysis or analyzed non-parametrically as required.

The primary analysis will be *intent to treat* including all women randomized and taking at least one dose of the experimental/placebo therapies with data carried forward. For practical reasons, only those with at least 14 days of Daily Perimenopause Diary or Calendar data will be included in any diary-based outcome measures (one week of baseline and one week of therapy).

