## **Amendment #4 (PRIMARY OUTCOME)**

We will also do subgroup analyses of VMS Score by Early Perimenopause (no skipped period or <60 day cycle length) and by Late Perimenopause (those with skipped or ≥60 day cycle lengths).

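### The test for a different response in Early and Late Perimenopause does not separate phase from run-in severity

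*Combined protocol and SAP*

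**What the plan says.** The primary outcome (section 2.8, PRIMARY OUTCOMES) is the daily VMS Score in points, "summarized as a daily average during the final 28 days of therapy with average run-in scores as a covariate". Section 2.16 specifies ANCOVA by therapy, "phase of perimenopause (Early/Late) and the interaction of therapy with phase, with baseline outcome variable as a covariate". It gives the interaction its purpose: "The interaction term will assess the possibility that the response to therapy differs between those in Early and Late Perimenopause". No therapy-by-run-in term is listed. After assumption checks, "data will be either transformed prior to analysis or analyzed non-parametrically as required"; no transformation is named, and the clause is not tied to the phase comparison.

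Amendment #4 adds: "We will also do subgroup analyses of VMS Score by Early Perimenopause", and likewise for Late.

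Two background statements bear on this:
- Section 1.1, on the earlier postmenopausal trial, reports VMS Score improvements of 52% on OMP and 22% on placebo, with significant interactions: "those who had more frequent/intense VMS at baseline showed greater treatment benefits from progesterone compared with placebo". This held for Score and for Frequency.
- Section 2.2 says the "natural history is for hot flushes to be variable and to increase over time to a maximum during the final year without flow".

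No section gives a run-in VMS Score by phase.

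**The concern.** An additive run-in covariate adjusts the level of the final Score. It does not adjust the size of the treatment difference. If the benefit in points grows with run-in severity, as the earlier trial indicates, and the phases differ in run-in severity, then therapy by phase picks up part of the therapy-by-run-in effect that was left out of the model.

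A gap between the phases is plausible. The final year without flow lies in Late Perimenopause, whereas Early includes women who still cycle regularly.

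The first principal question names both phases. A contrast driven by starting severity could be read as a property of the phase: that Early women respond less, or that OMP helps one group and not the other. The planned output would not let a reader tell these explanations apart.

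**Working it through.** **The plan's own figures.** Section 2.11 uses an effect size of 0.48 (3/6.25 = 0.48), two-sided alpha 0.05 and power 0.80. A two-sample t-test needs 70 per arm, and 140/0.8 = 175, as stated. For Amendment #6, a 3-point difference with SD 9 x sqrt(1 - 0.56^2) = 7.46 needs 98 per arm, and 196/0.8 = 245, as stated. The amendment's wording describes about 9 as already adjusted, so both 7.46 and 9 are carried below.

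**Inputs.**
- Evaluable women: 245 x 0.8 = 196. With an even phase split (assumed), that is 49 per arm within each phase.
- Effect: the final Score is 0.78 x run-in on placebo and 0.48 x run-in on OMP, in both phases. This applies the earlier trial's percentages to perimenopause (assumed).
- Run-in means (assumed): 4 per day x severity 2 = 8, from the entry frequency in section 2.5; 7 per day x severity 2 = 14, from the frequent/severe subgroup in section 2.8. Nearby values give the range.

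**Formulas.** Effect within a phase = (0.78 - 0.48) x run-in = 0.30 x run-in. Contrast c = 0.30 x (Late run-in - Early run-in). SE = SD x sqrt(2/49 + 2/49), which is 2.13 for SD 7.46 and 2.57 for SD 9. Chance of p<0.05 = 1 - Phi(1.96 - c/SE) + Phi(-1.96 - c/SE).

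| Run-in Early / Late | Effect Early | Effect Late | Contrast | p<0.05, SD 7.46 | p<0.05, SD 9 |
|---|---|---|---|---|---|
| 8 / 8 | 2.4 | 2.4 | 0 | 5% | 5% |
| 8 / 10 | 2.4 | 3.0 | 0.6 | 5.9% | 5.6% |
| 8 / 12 | 2.4 | 3.6 | 1.2 | 8.7% | 7.5% |
| 10 / 15 | 3.0 | 4.5 | 1.5 | 10.8% | 9.0% |
| 8 / 14 | 2.4 | 4.2 | 1.8 | 13.5% | 10.8% |
| 7 / 14 | 2.1 | 4.2 | 2.1 | 17% | 13% |

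**Does the covariate remove it?** No. In a simulation of the planned ANCOVA (4,000 trials per scenario, lognormal scores, run-in to final correlation 0.52-0.64), the contrast in favour of Late was 0.60, 1.20 and 1.75 points for 8 versus 10, 12 and 14, almost exactly the formula values. Rejection at 8 versus 14 was 20%, above the table because the simulated residual SD was only 5.2.

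**Does a therapy-by-run-in term help?** At 8 versus 14 the contrast fell from 1.75 to 0.10 points, with 5.3% significant. With a noisier run-in mean, 0.75 of 1.85 points remained, with 6.0% significant. With one third of women Late, rejection fell from 26% to 7.8%. The correction is large but incomplete.

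**Amendment #4 subgroups.** At 8 versus 14, power within phase is 0.26-0.36 in Early and 0.64-0.80 in Late (SD 9 to 7.46). Significance in Late but not in Early has probability 0.64 x 0.74 = 0.47 to 0.80 x 0.64 = 0.51. With a run-in mean of 11 in both phases (3.3 points each, power 0.44-0.59) it is 0.44 x 0.56 = 0.25 to 0.59 x 0.41 = 0.24.

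**The case against.** Four arguments stand against pressing this further.

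1. **Section 2.16 allows transformation.** A reader might infer that the plan is fixed on raw points. It is not. In data simulated with a proportional effect, residual checks on the raw ANCOVA failed in nearly every trial, so the clause would probably be invoked, and a log analysis would remove the artefact. What remains is that no transformation is named and a non-parametric analysis is equally permitted. The clause may reduce the problem but does not address it.

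2. **Points are a legitimate scale.** Section 2.11 defines clinical importance as 3 points. If Early women gain 2.4 points and Late women 4.2, the absolute benefit does differ. This stands. The issue is only whether the difference is attributed to phase or to starting severity.

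3. **A log-scale test is not neutral.** A reader might infer that it should decide the question. Under a constant 3-point benefit with unequal run-in, simulated log tests rejected therapy by phase in 11-25% of trials at gaps from 8 versus 12 to 7 versus 14, in the opposite direction, while the raw test stayed at 4-6%. The earlier trial shows benefit rising with baseline, not strict proportionality. This rules out log as the deciding scale. The companion term held rejection at or below 5% under the constant effect as well.

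4. **The run-in gap is undocumented.** Section 2.2 describes natural history, not trial entrants, and the same entry rule applies to both phases, which should narrow any gap. This stands, and it makes the point conditional.

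**Conclusion.** The point holds as a conditional weakness in how the phase question is answered. If run-in Scores differ by phase and the benefit rises with run-in, the therapy-by-phase contrast mixes the two. Its size under an equal-percentage effect is 0.30 points per point of run-in gap, with significance in about 6-17% of trials. That range rests on assumed run-in means, an even phase split, 196 evaluable women and an SD of 7.46-9. With equal run-in means there is no distortion.

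A reader might go further and infer that OMP will appear better in Late. That is true only in expectation and only if Late women start higher. Error rates of 25-37% can be produced by simulation, but they need run-in means of 5 and 15, with residual SD 5.7-7.9. An Early mean of 5 lies below the 4 x 2 = 8 implied by the frequency criterion at severity 2, and the documents do not support such a gap. Nor does this bear on the overall OMP-placebo comparison, for which the trial was sized.

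**What to change.** - **Section 2.16:** keep the planned raw-point model. For VMS Score and Frequency, add a companion model with a centred therapy-by-run-in term beside therapy by phase. Attribute a difference in response to phase only if therapy by phase persists in that model.
- **Amendment #4:** show mean run-in Score by phase, and give the Early and Late effects as OMP/placebo ratios beside the points. These are supporting description, not the deciding test. Do not infer a phase difference from one subgroup being significant and the other not.
- **Status:** the ethics board letter of 18 November 2018 says that the database was locked and statistical analysis had occurred. Label any added analysis post hoc.

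The cost is one degree of freedom, slightly less power for the interaction, and a few more lines in the report. No new data are needed. The correction is incomplete when the run-in mean is noisy, and the report should say so.
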